**Abstract:** Recently there has been compelling evidence that inflammatory bowel disease (IBD) subjects, both Crohn's disease (CD) and Ulcerative Colitis (UC), commonly have disrupted sleep, and disrupted sleep correlates with the risk of disease flare. Sleep/wake cycle, immune function, metabolism and multiple biological processes are all orchestrated by circadian rhythms. Circadian misalignment between the central circadian clock in the brain and environment has been found to contribute to a variety of metabolic and gastrointestinal tract (GIT) diseases. Yet, the prevalence and impact of circadian misalignment on IBD disease activity and GIT mucosal inflammation have not been established. The long-term objective of our research is to investigate the hypothesis that circadian malalignment worsens GIT mucosal inflammation and disease course in IBD. To test this hypothesis, we will conduct a prospective in lab study with human subjects on the impact of circadian misalignment in left sided mild to moderate Ulcerative Colitis. We will perform two circadian measures phase assessments under strictly controlled laboratory conditions at: 1) baseline, and after 2) circadian misalignment after three days of simulated night shifts in both inactive UC patients and healthy control subjects. To test the hypothesis that UC patients (compared to healthy subject controls) are less resilient to circadian misalignment we will assess: time impact of our protocol on circadian rhythms (Aim 1) by the following: phase angle of entrainment [time from dim light melatonin onset to sleep onset] (Aim1a); peripheral circadian rhythms by clock gene expression in colonic tissue from a flexible sigmoidoscopy and in subjects peripheral blood mononuclear cells (Aim1b); and colonic clock gene expression and Per2::Luc activity over 24 hours utilizing an in-vitro model of colonic organoids (Aim1c). Next, we will test the hypothesis that circadian misalignment will increase colonic permeability and mucosal inflammation in UC patients (vs. Controls) (Aim2) through the following: endoscopy score, stool calprotectin, colonic barrier (permeability, AJC proteins), and markers of systemic barrier function and inflammation (Aim 2a); adversely impacting microbial community structure/function (Aim 2b); and use 2D colonic organoid monolayers to explore ex-vivo barrier function by co-culturing with TNF- $\alpha$ /INF- $\gamma$  (Aim

2c). The results of this innovative proposal will greatly increase our understanding of the important role circadian misalignment may have in UC disease activity and colonic inflammation, and identify new circadian regulated targets for treatment in UC.

**Objective:** The long-term objective of our research is to investigate the hypothesis that circadian misalignment worsens intestinal mucosal inflammation and disease course in IBD. Key evidence supporting this hypothesis include that disruption of circadian rhythms in the host impacts the intestinal barrier, microbiota composition, and mucosal/systemic immune function, all critical factors in the pathogenesis of IBD. Data from rodents generated by our group and others show that disruption of the light: dark cycle (a model of shift work) or genetic circadian rhythm disruption (of a core clock gene) changes the intestinal microbial community, alters the production of microbial products like short chain fatty acids (SCFAs) resulting in colonic hyperpermeability through disruption of the apical junctional complex (AJC) in colonic IECs, increased mucosal inflammation, culminating in a more pro-inflammatory state in the intestine. In humans, shift work increases susceptibility of the colonic barrier to an injurious agent like alcohol and increases systemic pro-inflammatory cytokines IL-6 and IL-1 $\beta$  and that chronic alterations in light:dark cycles in mouse models of IBD increase colitis severity and mortality. In humans with IBD, our group and others have shown that a later chronotype (Fig. 2A) and high variability in rest-activity rhythms (Fig. 2B) (both markers of circadian misalignment) are associated with worse IBD disease course, increased colonic permeability, alterations in the intestinal microbiota community (dysbiosis), and reduced colonic circadian clock gene expression. Therefore, the immediate goal of this proposal is to elucidate the mechanisms of colonic inflammation induced by circadian misalignment in UC. This will be the first comprehensive examination of human circadian rhythms in IBD.

**Hypothesis:** Circadian misalignment worsens intestinal mucosal inflammation and disease course in IBD.

**Specific Aims:**

- Aim 1: Test the hypothesis that circadian misalignment is more prevalent in UC compared to healthy controls and that UC patients are more susceptible
- Aim 2: Test the hypothesis that circadian misalignment increases colonic permeability and mucosal inflammation through disrupting the AJC and adversely impacting microbial community structure / function in UC.

**Background:** A.1. IBD is Associated with Sleep Disruption. Crohn's Disease (CD) and Ulcerative Colitis (UC), collectively known as inflammatory bowel disease (IBD), are two devastating chronic diseases of the gastrointestinal tract (GIT). IBD is typically diagnosed at an early age, has no known cure, and has a chronic relapsing and remitting disease course that includes

disabling symptoms during periodic flare ups. IBD affects over 1.5 million individuals in the US with an estimated direct cost of \$14 to 31 billion (31, 32). IBD has a heterogeneous disease course that commonly has an aggressive phenotype. Identifying risk factors that can trigger disease flare and aggressive disease course are essential to avoid complications such as hospitalizations and surgery and are critical to improve disease course and patient quality of life. Factors that are associated with a more aggressive disease course include the use of prednisone or inability to wean off prednisone (steroid dependency), early age of diagnosis, hospitalization, need for IBD surgery, and the presence of fistulizing/stricturing perirectal disease in CD (33-35). However, these factors cannot fully explain the disease course in many patients. Recently, there has been an increased awareness of the high prevalence of sleep disruption in IBD. Our group was one of the first to report a high prevalence of sleep disturbances in IBD, (17, 36) and patients with IBD exhibit disrupted sleep (polysomnography) even when their disease is inactive. A subsequent prospective cohort showed that ileo-cecal inflammation in CD correlates with poor sleep. In essence, IBD patients in clinical remission with poor sleep had higher subclinical disease activity compared to those IBD patients reporting good sleep. Thus, disrupted sleep/wake cycles, an important output of the circadian clock, can be one factor that triggers disease flare and promote progressive disease course; yet the impact of circadian rhythm disruption on disease pathogenesis has not been fully evaluated, which is one of the goals of this application.

**A.2. Circadian Rhythms are Critical to Health.** Sleep, rest-wake activity, and multiple biological processes such as metabolism, (37) cell proliferation, (38) and immune activity are orchestrated by the circadian clock on a roughly 24h cycle. The discovery of the core molecular machinery of the master or central circadian clock in the suprachiasmatic nucleus (SCN) which consists of a transcription and translation feedback loop of positive factors (e.g., Clock, Bmal1) and negative repressors (e.g., Per1, Per2, Cry1, Cry2) has led to a number of key mechanistic discoveries regarding the circadian clock machinery and its functions that are critical for normal physiology and behavior. Synchronization of internal circadian clock with external environmental cues (e.g., light) is critical for good health, which is not surprising as the circadian clock is known to control the expression of 10-20% of the genes in the human body. In addition, peripheral clocks that contain the same core molecular machinery as in the SCN are found in cells of every organ in the body, including colonic IECs in the GIT. The GIT exhibits diurnal rhythms in many physiologic functions such as motility, intestinal transport, and IEC replication all of which are governed by inputs from the SCN as well as other signals that entrain the circadian clock in the GIT such as time of food consumption. Circadian misalignment is a mismatch between the environmental cues (e.g., light) and the central clock in the SCN or a mismatch between the central and peripheral clocks which can occur due to shift work or consumption of a high fat diet, respectively (54, 55). Modern 24h society, with increased nighttime light exposure, light pollution, the increasing

prevalence of shift work, and nighttime eating have made misalignment of our endogenous circadian rhythms more common. There are multiple causes for human circadian misalignment including shift work, long distance travel with jet lag, and perhaps the most common: social jet lag, which is changing the midpoint of sleep more than 2h between work and work-free days due to social obligations. The most well-studied model of circadian misalignment, shift work, is now estimated to include 15 million workers in the US. Not surprisingly, shift work is associated with a number of GIT disorders and diseases including irritable bowel syndrome, peptic ulcer disease, and colon cancer. Therefore, it is possible that circadian misalignment may be one factor that promotes intestinal inflammation and disease flare in UC.

A.3. IBD is characterized by Intestinal Barrier Dysfunction and Inflammation. The intestinal barrier is the largest interface between the body and the environment and must be selectively permeable to restrict pro-inflammatory microbiota and microbial products but at the same time allow passage of nutrients, electrolytes, and water. Thus, integrity of the intestinal barrier is critical for maintaining good health. Indeed, disrupted intestinal barrier function (“leaky gut”), endotoxemia (i.e., high levels of systemic lipopolysaccharide (LPS)), and subsequent production of pro-inflammatory cytokines and reactive oxygen species are all hallmarks of IBD. In fact, fluctuations in intestinal barrier function in IBD is an established predictor of disease flare in CD and UC. Several environmental factors can disrupt the intestinal barrier function in IBD like medication, alcohol, and stress but this only occurs in a subset of individuals suggesting that resiliency of the intestine determines the impact of these environmental factors in chronic inflammatory disorders like IBD. The intestinal barrier consists of the apical junctional complex (AJC), both tight junction (TJ) and adherens junction (AJ) proteins, that links the IECs and seals the paracellular space to prevent translocation of pro-inflammatory bacteria and bacterial components such as LPS into the intestinal mucosa. IECs turnover every 4-5 days, replenished by a small population of intestinal stem cells (ISCs), and IEC regeneration and differentiation are essential to maintain barrier homeostasis. It has also been established that alterations in gut microbiota are another hallmark of IBD, and perturbation of the structure of the microbiome can disrupt the intestinal barrier and cause intestinal inflammation in IBD. Specifically, in IBD there is a decrease in bacterial diversity and temporal stability with a loss of bacteria in the Firmicutes phylum^79 and increase in Proteobacteria. It is not understood if alterations in the intestinal microbiota are the cause of or result from increased intestinal permeability and inflammation, but IBD is characterized by both barrier dysfunction and dysbiosis. Disruption of central or peripheral circadian rhythms is sufficient to impact both the intestinal barrier and the microbiota; therefore, it is important to determine if circadian misalignment is sufficient to induce changes in the GIT that promote intestinal inflammation and UC disease flare.

A.4. Circadian Rhythms are Critical to Maintain the Intestinal Barrier. Intestinal barrier homeostasis is mediated by cross-talk between IECs and the intestinal microbiota. This cross-talk occurs via multiple mechanisms including interactions with toll-like receptors (TLRs) on the IECs. There are multiple lines of evidence in cell lines, animal models, and human studies that support the scientific premise that disruption of circadian rhythms in the host negatively impacts intestinal barrier integrity: (1) alcohol (0.2%) increases the expression of the circadian clock genes Clock and Per2 in a human IEC line (Caco-2 cells), and knock down of Clock or Per2 gene expression by siRNA prevents alcohol-induced barrier dysfunction, (2) chronic disruption of the central clock by either disruption of light:dark cycles or a mutation in the core circadian molecular clock (i.e., Clock mutant mice) increases intestinal permeability and endotoxemia, (3) healthy night workers who consume alcohol (0.5g/kg daily for 7 days) have increased colonic permeability compared to healthy day workers consuming alcohol, and colonic permeability inversely correlates with decreased plasma melatonin over 24h, (4) our lab and others show that circadian misalignment in the host causes microbial alterations with a decrease in bacteria (Firmicutes) that produce short chain fatty acids (SCFA) like butyrate (Bu), and (5) the core clock machinery (Bmal1) regulates IEC cell regeneration and barrier homeostasis. Taken together, these studies strongly support the concept that circadian misalignment could promote IBD flare via a mechanism involving disrupting the colonic barrier and intestinal microbiota dysbiosis.

A.5. Circadian Rhythms and IBD. Given that the circadian rhythms of the host can impact colonic barrier integrity, it is likely to also impact chronic inflammation in IBD; however, the impact of circadian misalignment in humans with IBD has not been investigated. Prior work in animal models of IBD by our group and others show that chronic disruption of central circadian rhythms in the host by shifting light:dark cycles causes significantly worse colitis and increases mortality by Dextran Sodium Sulfate (DSS) (Fig. 1) or by Dextran sodium sulfate/2,4,6-trinitrobenzene sulfonic acid (TNBS). In addition, we recently found that an intestinal specific Bmal1 knock out mice develop worse DSS colitis with increased permeability despite normal central circadian behavior (Fig. 1C&D) suggesting that influencing circadian rhythms in the GIT are sufficient to impact the barrier and mucosal inflammation. Furthermore, a Per2 mutant mouse with increased Per2 activity had constitutively high levels of the tight junction proteins (TJP) occludin and claudin-1 in the colon, is resistant to DSS-induced colitis. In humans, genetic analysis found an association between polymorphisms in one of the core circadian clock genes Period 3 (Per3) and increased incidence of Crohn's disease. Our group has conducted several studies in humans with IBD to examine the role of circadian rhythms: 1) We examined the association between chronotype (category of circadian timing) and IBD using two validated questionnaires – the Owl and Lark and Munich. We found that a later chronotype is associated with a worse IBD quality of life, IBD subjects on aggressive medications (biologics) had a later midpoint of sleep, and Crohn's subjects with increased social jet lag are more likely to have a

history of fistulizing or stricturing disease (Fig 2A). These data suggest that circadian rhythms are associated with IBD disease phenotype. 2) Our examination of endogenous salivary melatonin secretion in four subjects with inactive IBD, revealed that two of the subjects had low melatonin secretion compared to controls and the one had an arrhythmic profile, indicating circadian abnormalities are present in IBD patients. 3) We used wrist actigraphy to identify variations or instability in rest-wake activity that correlate to central circadian rhythms in inactive IBD subjects and found that there was less interdaily stability in IBD subjects with an aggressive disease course (history of fistulizing/stricturing disease in CD and history of surgery, steroid dependence, or biologic use in UC and CD ) and greater interdaily variability correlated with increased colonic permeability (Figs. 2B, 2C). 4) Examination of stool microbiota in inactive IBD subjects reveals changes in the microbiota that were associated with circadian misalignment. For example, there is a significant decrease in SCFA-producing bacteria (Fig. 2D) and bifidobacterium longum which has been used as a treatment in active UC. Taken together, these findings support the hypothesis that circadian rhythms influence the intestinal barrier and the intestinal microbiota; however, no human studies have comprehensively studied the central or peripheral circadian rhythms in IBD subjects by the gold standard in the field (DLMO) while examining subclinical inflammation and colonic barrier function, which is one of the goals of our current study.

**A.6. Importance of the Proposed Research.** There is a clear scientific rationale and crucial need to take the next step and more comprehensively assess central and peripheral circadian rhythms in IBD in order to determine the impact of circadian misalignment in IBD on colonic mucosal inflammation, subclinical systemic inflammation, barrier function, and intestinal microbiota. In the proposed study, we will determine if patients with inactive UC have circadian misalignment of central and/or peripheral circadian rhythms and if they are more susceptible to circadian misalignment after a simulated night shift (Specific Aim 1) and determine if circadian misalignment impacts colonic barrier integrity and intestinal microbiota (Specific Aim 2). We selected UC as a model of IBD because: (1) it always affects the rectum/sigmoid, thus it is relatively easy to access and obtain the required colonic intestinal tissue through sigmoidoscopy, (2) microbiota-directed interventions like fecal microbiota transplant (FMT) appear to be more promising in UC than in CD, and (3) our data support that circadian misalignment has a substantial impact on the colonic barrier in UC subjects. The knowledge gained from the proposed studies is likely to lead to the identification of new mechanisms of how circadian misalignment promotes chronic inflammation in IBD, and allow for the study of new chronobiological therapeutics in IBD that target circadian misalignment such as bright light therapy, exogenous melatonin, or other molecular targets associated with circadian misalignment induced in IBD.

**Research Design:** 40 human subjects will be recruited into this proposed study: 20 Healthy Controls and 20 UC subjects with left sided inactive disease (Mayo Score  $\leq 2$ ) on stable medications. All subjects (UC and HC) will undergo a full medical history and physical examination including a blood draw for the screening visit. A urine drug screening will take place on the subject's first day at the sleep laboratory. Subjects who wish to participate will have the study explained by the coordinator and will then sign a Rush IRB-approved informed consent. All UC subjects will complete a validated questionnaire regarding disease-specific symptoms (Mayo Score) to determine they are inactive and may be enrolled in the study.

In addition, subjects will provide basic demographic data, UC history if appropriate, UC disease activity status as detailed further above, and the Munich Chronotype questionnaire. All subjects will complete a validated 3-month food frequency questionnaire (FFQ) to collect dietary information (1). 40 participants (Specific Aims 1-2) will be enrolled for the within-subject prospective in-laboratory study protocols. Participants will be young (18-50 y), healthy, non-diabetic, non-obese, Caucasian/African American/Asian and non-Hispanic/Hispanic in ratios consistent with the population of Chicago, and without medication use (excepting oral contraceptives) for HC. HC and UC subjects will be matched according to age ( $\pm 3$  years), sex, race, and BMI ( $\pm 3$  kg/m^2). UC subjects will be on stable medications with no recent use of prednisone or antibiotics for the last 3 months. After signing an informed consent, the subject will fill out questionnaires, start a food diary, and sleep diary, and have 2 weeks of wrist actigraphy before their seven-day in lab session in the Clinical Chronobiology Center (CCC). Since participants will be in the sleep lab for 7 days and isolation can cause an increase in depression and anxiety, a normal psychological evaluation is part of the inclusion criteria for this study. This will be determined based on how participants respond on the BDI and STAI questionnaires, which assess depression and anxiety. The study physician will review the questionnaire responses and evaluate if the participant will feel comfortable staying in the lab for 7 days.

**Subject Characteristics:** We will recruit (1) 20 HC subjects without any medical illnesses (2) 20 subjects with biopsy proven UC, inactive (Mayo Score  $\leq 2$ ) on stable medications and no disease flares for  $> 3$  months. HC and UC subject will be matched according to age ( $\pm 3$  years), sex, race, and BMI ( $\pm 3$  kg/m^2).

**Sample Size Analysis:** All power estimates were computed using R package pwr, and we assume a Type I error rate of 0.05 and a 2-sided test for all analyses. Power estimates were derived from the data from my prior K grant. The primary endpoints of this study will be phase angle/DLMO (Aim 1) and colonic permeability (13-24h urinary sucralose) (Aim 2). For Aim 1, we found a  $\sim 2$ h phase advance in DLMO in NW compared to DW at -0.2 (SD=2.1) compared to -4.34 (SD=3.8), respectively. With a sample size of 20 in each group (10 men/10 women), this

provides an 86% power to detect differences in DLMO, but 98% power if sex is pooled. For Aim 2, we found a 40% increase in colonic permeability in night shift workers compared to day workers after moderate alcohol consumption at 0.57 compared to 0.11 (SD=0.20). With 20 subjects, this will give us a 84% power to detect a difference in colonic permeability between the two groups for each sex and if sex is pooled will give us a 97% power with a two-sided two-sample t-test at alpha=0.05 level. These conservative estimates provide a good estimate of the power to detect differences in phase angle and colonic permeability between UC patients before and after simulated night shifts. We anticipate we will have nonparametric data and will use the Wilcoxon match-pair test for analysis of colonic permeability, inflammatory cytokines, and markers of endotoxemia. Order effects will be used as a covariate in multivariate analysis with analysis of variance (ANOVA) and linear regression as indicated. Microbiota data analysis is described above. Non-parametric analysis of actigraphy data will be analyzed with the nparACT package. In our periodogram analysis of time series data we will use Fast Fourier Transform Non-linear Least Squares (FFT-NLLS), a nonlinear least-squares algorithm of a times series typically used for luminescence data (149) and analyzed with Biodare software (150). Data will be presented as mean  $\pm$  SEM for variables that can be considered normally distributed (or median and range for variables not normally distributed). All analyses will use R (v.3.2.5), Biodare 2, and SPSS (SPSS Inc., Chicago, IL).

**Inclusion Criteria:** *Study will include individuals that are;*

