**Healthy Controls:**

1. M/F, 18-50 y/o, age  $\pm$  3y sex, race, and BMI ( $\leq$  3 kg/m^2) match with UC subject
2. No clinical evidence of any medical illness
3. Normal psychological evaluation based on question responses and negative drug screen (See Below)

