**Ulcerative Colitis:**

1. Patients with other forms of colitis such as Crohn's disease (CD) or indeterminate colitis
2. Patient with active UC (Mayo  $> 2$ )
3. Pancolonic UC (colitis past the splenic flexure, Montreal E3))
4. Gastrointestinal surgery
5. Other GI diseases or systemic diseases (cardiac, renal failure, cirrhosis)
6. Shift work in the last 6 months
7. Antibiotic use within last 12 weeks
8. Patients who have used anti-diarrheal agents such as Lomotil or Imodium within 3 days of the study
9. Prednisone use the last 30 days
10. Significant Depression (score  $\geq 14$  BDI)
11. Significant Anxiety (score  $\geq 40$  STAI)
12. Use of probiotic supplement in last 4 weeks except yogurt.
13. Intentional change in diet.

14. Chronic use of NSAIDS. A washout period of 3 weeks is needed before the subject could be enrolled into the study. Low dose aspirin is allowed.
15. Chronic Alcohol use. A washout period of 3 weeks is needed before the subject could be enrolled into the study.
16. Have children under 6 months

**Subject Recruitment:** All Human UC subjects will be recruited at the RUMC Digestive Disease Clinic and the Rush Crohn's and Colitis Center by the PI or Clinical Coordinator. Healthy control subjects will be recruited by established recruiting methods, which we have successfully used over the past ten years, including notices to local organizations and internet, newspaper, and radio advertising. Based on our experience, of the initial calls made by potential subjects, 15% remain interested in the study after they are informed of study procedures. Of these individuals, 70% pass an initial telephone screening (in which questions are asked about medical condition, current medication use and work and travel history). Of those remaining individuals, 33% pass the medical and psychological screening (described below), and of these, 70% complete the study.

In this study we will recruit 40 Human Subjects in the following two groups:

- 1) Ulcerative Colitis (UC) (n=20).
- 2) Healthy Controls (HC) (n=20).

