**Figure 1. Outcome Measures**

Aims	Outcome Measure	Test	Assessment	Statistical Test
Aim 1	Primary	Phase Angle of entrainment (DLMO – sleep onset)	Baseline	ANOVA
			Misalignment	
	Secondary	Clock gene expression in PBMCs	Baseline	Cosinor Analysis, Mixed Model ANOVA
			Misalignment	
Aim 2	Secondary	Urinary Melatonin	Baseline	Wilcoxon signed-rank test
			Misalignment	
	Exploratory	Clock gene expression and Per2::LUC in Colonic Organoids	Baseline	Cosinor Analysis, FFT-NLLS
			Misalignment	
Aim 2	Primary	Intestinal Permeability (i.e. 12-24 h Urinary Sucralfate)	Baseline	Mann-Whitney U test
			Misalignment	
	Secondary	Mayo Score (Endoscopy)	Baseline	Wilcoxon signed-rank test
			Misalignment	
	Secondary	Stool Calprotectin	Baseline	Wilcoxon signed-rank test
			Misalignment	
Aim 2	Secondary	Serum cytokines (IL-6, TNF- $\alpha$ )	Baseline	Repeated measures ANOVA
			Misalignment	
	Secondary	Fecal Microbiota	Baseline	Principal Coordinate Analysis
			Misalignment	
Aim 2	Secondary	Serum LBP, LPS, zonulin, sCD14, metabolomics	Baseline	Repeated measures ANOVA
			Misalignment	
	Exploratory	TER in 2D Colonic	Baseline	ANOVA

		Organoids with ex-vivo TNF- $\alpha$ /INF- $\gamma$	Misalignment	
Exploratory		RNA seq of Colonic Organoids	Baseline	JTK Cycle
			Misalignment	

**Safety and Adverse Events:** We have identified five key potential risks to human subjects in this study:

1. Risk to Confidentiality and Record-Keeping of patient personal health information (PHI).
2. Risk of potential side effects associated with Phlebotomy (blood draw).
3. Risk of potential side effects associated with Sigmoidoscopy and Colonic Biopsy.
4. Risk of potential side effects associated with completion of the Questionnaires.
5. Risk of potential side effects associated with in lab study

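### Controls are individually matched to UC subjects, but no stated analysis of the Aim 2 primary uses the match; if matched subjects have correlated outcomes, the UC-HC comparison is conservative

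*Combined protocol and SAP*

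**What the plan says.** **Matching.** Research Design states that "HC and UC subjects will be matched according to age" (within 3 years), sex, race and BMI (within 3 kg/m²). Subject Characteristics and Data Analysis Methods repeat this. The inclusion criteria for healthy controls require each control to "match with UC subject", so the matching is individual.

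**Tests for the Aim 2 primary.**
- Figure 1 gives "Mann-Whitney U test" for intestinal permeability.
- Sample Size Analysis bases Aim 2 power on a "two-sided two-sample t-test at alpha=0.05 level".
- The same section says the study "will use the Wilcoxon match-pair test for analysis of colonic permeability, inflammatory cytokines, and markers of endotoxemia". It does not define the pairing unit. The sentence just before it concerns differences "between UC patients before and after simulated night shifts".

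**Error rate.** Sample Size Analysis says "we assume a Type I error rate of 0.05 and a 2-sided test for all analyses".

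**Completion.** Subject Recruitment ends its account of screening yield with "of these, 70% complete the study".

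The only covariate named in Sample Size Analysis is order. No section carries the matched pair, or the matching variables, into the permeability analysis.

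**The concern.** Matching on four factors makes recruitment harder in a 40-subject study with a seven-day laboratory stay. If it works, matched subjects resemble each other on the outcome, and the UC-HC difference has a smaller variance than two independent groups would give. A test that treats the groups as independent then uses a standard error that is too large. Its p-value and interval for the UC-HC difference are conservative, and some of the precision gained by matching is lost.

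There is also a gap in specification. One primary endpoint has an unpaired test in Figure 1 and a paired test in Sample Size Analysis, and neither is tied to a stated contrast. A reader cannot tell whether the primary question is UC against HC on one test day, before against after within UC, or the difference between groups in the change.

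**Working it through.** **1. The plan's own power.** The Aim 2 inputs are 0.57 against 0.11 with SD 0.20, so d = (0.57 − 0.11)/0.20 = 2.30. Two-sample t-test power (noncentral t, two-sided 0.05) is above 99.9% at 20 per group, where the plan states 97%. It is 99.8% at 10 per group, where the plan states 84%. The stated figures do not reproduce. A power of 97% at 20 per group implies d = 1.25.

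**2. Effect of ignoring the pairs on one test day.** Let ρ be the within-pair correlation. It is not in the documents, so it is assumed. With n pairs and common SD σ:
- the unpaired test uses variance 2σ²/n;
- the true variance of the difference is 2σ²(1 − ρ)/n;
- the standard error is therefore overstated by the factor 1/√(1 − ρ).

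Simulation results (20 pairs, bivariate normal, 20,000 runs). Power is shown as Mann-Whitney / signed-rank on the matched pairs:

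| ρ (assumed) | SE factor | Type I error, Mann-Whitney | Power, d = 0.8 (assumed) | Power, d = 1.25 | Power, d = 2.30 |
|---|---|---|---|---|---|
| 0 | 1.00 | 5.0% | 67.7 / 65.5% | 96.3 / 95.5% | about 100% both |
| 0.1 | 1.05 | 4.0% | 67.4 / 69.3% | 96.6 / 96.8% | about 100% both |
| 0.3 | 1.20 | 2.3% | 69.6 / 80.1% | 98.2 / 99.2% | about 100% both |
| 0.5 | 1.41 | 0.9% | 72.4 / 91.2% | 99.2 / 99.9% | about 100% both |

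At ρ = −0.2 the direction reverses, and the Mann-Whitney type I error is 7.3%.

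At an assumed d = 0.9 and ρ = 0.3, unpaired power is 83% (t-test) or 81% (Mann-Whitney). For the paired t-test the standardised difference is 0.9/√(2 × 0.7) = 0.76, and power with 20 pairs is 89-90%.

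**3. Why a pair-only test is not the answer.** Assume that the 70% completion applies independently to each subject, with no replacement. Complete pairs are then 0.7² × 20 = 9.8, about 10, against 0.7 × 20 = 14 subjects per group. At d = 0.9 and ρ = 0.3, power is about 54-56% for a strict paired test, 63-64% unpaired, and 73-74% for an analysis that uses the pairs and keeps unpaired subjects. The last figure is somewhat optimistic. The 73% takes ρ as known. The 74% estimates ρ, but with crude degrees of freedom null rejection was 6-7%, so a small-sample correction is needed.

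**4. The group-by-test-day contrast.** Suppose subject j of pair i has outcome on day t equal to fixed effects + pᵢ + sᵢⱼ + eᵢⱼₜ. The change from day 1 to day 2 removes both pᵢ and sᵢⱼ. A random pair intercept therefore cannot sharpen the UC-HC difference in change. In one simulated complete dataset (20 pairs, pair variance 0.3) the interaction standard error was 0.289 with and without the pair effect, and the simulated correlation of matched subjects' changes was 0.00. The gains in steps 2 and 3 apply only to a comparison at one test day.

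**The case against.** The strongest objection is that the loss is hypothetical. It needs a clearly positive correlation in sucralose excretion between matched subjects, and the documents report none. Entry is already restricted to ages 18-50 and non-obese subjects, so matching may add little correlation. At ρ = 0 pairing costs 1 to 2 points of power. At the plan's own d = 2.30 nothing is lost, and at d = 1.25 about 1 point. The effects of 0.8 and 0.9 SD are assumptions. All of this stands, so the size can only be stated conditionally. The plan's large effect is weak reassurance, however. It compares night workers with day workers after alcohol, not UC with controls, and the stated powers do not follow from it.

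It may also be said that the plan already names a matched-pair test for permeability. It does, but the context points to before and after within subject, and the pairing unit is undefined. The documents do not support reading it as a test on UC-HC pairs.

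Three stronger readings are tempting and are not supported:
- **Power is certainly lost.** This depends on ρ and on the effect size.
- **The plotted error bars are too wide.** Per-group mean ± SEM, or median and range, do not depend on the test. Only the interval and p-value for the UC-HC difference do.
- **The result would be invalid.** With positive correlation the unpaired test errs on the cautious side. Only a negative correlation would inflate its error rate.

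Finally, the 70% comes from a description of recruitment yield and does not rule out replacement, so about 10 intact pairs is a scenario and not a forecast.

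**Conclusion.** The point holds in conditional form. Controls are individually matched, and nothing in the plan uses that match for the Aim 2 primary. Figure 1 and Sample Size Analysis also name incompatible tests for the endpoint. If matched subjects are positively correlated, a one-day UC-HC test runs at about 4%, 2% or 1% instead of 5% for ρ of 0.1, 0.3 or 0.5. At an assumed 0.9 SD and ρ = 0.3, it gives up roughly 6 to 9 points of power (80-83% against 89%). The loss is nil at ρ = 0 or at d = 2.30, and about 1 point at d = 1.25. This is a matter of precision and of an incompletely specified primary test, not of bias. It is worth correcting because the matching data will already be collected.

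**What to change.** 1. State the primary UC-HC contrast for permeability, and reconcile the tests in Figure 1 and Sample Size Analysis. If the Wilcoxon test is meant for before and after within subject, say so.
2. Replace Mann-Whitney with one model on all available subjects, with sucralose on a log or rank scale. Include group, test day, their interaction and a subject effect. Add either adjustment for all four matching variables (age, sex, race, BMI) or a matched-pair effect. Use small-sample degrees of freedom such as Kenward-Roger.
3. If the primary contrast is the group-by-test-day difference, a random pair intercept alone is not enough. Let the matching act on the change, through a pair-by-day effect or through the matching variables by test day.
4. Do not use a strict pair-only test, because it discards every subject whose partner does not complete.
5. Recompute power for the stated contrast, over a range of within-pair correlations that includes zero.

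The cost is SAP wording, slightly more analysis work and a few degrees of freedom. No new data are needed. If the within-pair correlation is near zero, about 1 to 2 points of power are lost.
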